Statistical Analysis Plan

Effect and Cost-effectiveness of the Everyday Life Rehabilitation Intervention

A pragmatic RCT of Everyday Life Rehabilitation - a person-centered, recovery- and activity-based intervention package for residents with severe psychiatric disability living in sheltered or supported housing facilities

[figure not shown]
ClinicalTrials.gov identifier	NCT05056415
SAP version/date	2.0, 24-01-03
Principal investigator, co-author of SAP	[name], Department of community medicine and Rehabilitation, Umeå university, Sweden
Responsible statistician, main author of SAP	[name], Department of public health and clinical medicine, Umeå university, Sweden

SAP revisions

Version 2.0 - 2024-01-03

- Page 6: Description of the internal pilot was revised as it now includes both wave 1 and 2, which was determined since wave included fewer participants/housing units than expected.
- Page 5: Sample size was recalculated based on data from the internal pilot including wave 1 and 2. The updated sample size calculation, based on internal pilot data, showed that the initial target sample size was not sufficient to detect a group difference of 5 points. The new revised power analysis was made for detecting a group difference of 10 points.

Signatures

[name], responsible statistician, and main author of SAP

[name], principal investigator and co-author of SAP

Content

SAP revisions.....	2
Signatures	2
Introduction.....	4
Background and rationale.....	4
Objectives	4
Study methods.....	4
Trial design.....	4
Randomization.....	4
Sample Size	4
Framework.....	5
Statistical interim analysis and stopping guidance.....	5
Timing of final analysis.....	5
Timing of outcome assessments	6
Statistical principles	6
Confidence intervals and P values	6
Adherence and Protocol deviations	6
Analysis populations	6
Trial Population.....	6
Eligibility.....	6
Recruitment	6
Withdrawal/ Follow-up.....	7
Baseline patient characteristics.....	7
Analysis	8
Outcome definitions	8
Analysis methods	8
Missing data.....	9
Additional analyses.....	9
Statistical software	9
References	9
Appendix – code for sample size recalculations.....	10

Introduction

The present statistical analysis plan (SAP) gives a detailed description of planned statistical analyses for the pragmatic cluster randomized controlled trial *Effect and Cost-effectiveness of the Everyday Life Rehabilitation*. The SAP is written with consistency with the guidelines published by Gamle et al (1).

Background and rationale

People with severe psychiatric disability (SPD) frequently experience overwhelming symptoms, disengagement, and difficulties handling daily life situations. Generally, SPD includes or results in low autonomy and a sedentary lifestyle. The person-centered, motivational, recovery-, and activity-based intervention model 'Everyday Life Rehabilitation' (ELR), integrated in sheltered and supported housing facilities for people with SPD, has shown promising outcomes in feasibility studies (2–6) on health- and activity-measures for residents/participants, based on pre-post-follow-up measures of Satisfaction with Daily Occupations (SDO), Assessment of Motor- and Process-skills (AMPS), Social Interaction (BSI-II) (Assessment of Social Interaction Skills – II), ADL-taxonomy with a 5-grade scale on effort, Symptom Checklist – 90 items (SCL-90), Goal Attainment Scaling (GAS), as well as self-narrated changes in hope, identity, and personal agency. However, the effectiveness of ELR has not yet been established in a RCT.

Objectives

The overall objective of the present project is to investigate the effectiveness on quality of life, self-perceived recovery, everyday functioning, and goal-attainment of ELR for people with SPD living in sheltered or supported housing facilities.

Study methods

Trial design

The trial is pragmatic cluster randomized trial with two parallel arms. Housing facilities, serving as clusters of eligible participants, will be randomized into ELR or treatment as usual (TAU). Recruitment of participants and randomization will be performed in two waves, starting the intervention in September of 2021 and 2022, respectively. The study has an adaptive design, where data from the first wave of the study will be used in an internal pilot with the purpose of investigating and improving feasibility and updating sample size requirements before continuing with the full-scale RCT. The internal pilot data will be included in the analysis of the full-scale RCT.

Randomization

Randomization will be performed separately at the two waves. The randomization will be stratified on municipalities, giving a 1:1 allocating ratio of housing facilities within each participating municipality. This is partly due practical reasons; the required education of occupational therapists and housing staff could be unfeasible if too many housing facilities within a municipality are in the intervention group. As the number of participants within each housing facility will vary, the allocation ratio of participants in the study will not be fully 1:1 balanced.

The randomization is performed by an independent statistician, otherwise not involved in the project, by generating a group allocation for all included housing facilities using a computer script. The list of the housing facilities and participants will be completely anonymized for the statistician.

Sample Size

The study was originally designed to detect a difference of 5 points on the ReQoL-scale. The minimum reliable change and minimum important difference has been suggested to be 10 points for ReQoL-20.

Assuming a standard deviation of 10 (2), an average cluster size of 2 participants per hosting facility and an intraclass correlation of 0.1, a total of 35 housing facilities in each group is required to reach a power of 80% when using a significance level of 5%.

The target sample size was updated after the internal pilot before the inclusion of housing facilities and participants in wave 3, based on outcome variability and intraclass correlation observed in the internal pilot.

The Monte Carlo simulation based on the statistical model from the pilot data showed that the initially planned sample size of 70 houses is sufficient to detect a difference of 5 points in the ReQoL scale with a power of only 53%.

Considering that recruitment to the study was somewhat slower than expected in wave 1 and 2, and that the sample size recalculations showed that more housing units will be needed than initially estimated to reach power for detecting a 5 points difference, it was decided to re-dimension the study to detect a difference of 10 points. Wave 3 and 4 will recruit additional 42 housing units. The average attrition rate of the ELR and TAU arms combined after wave 2 was 33%. The same attrition rate in wave 3 and 4 would thus render in a total of $42 * 0.67 = 28$ new housing units. Monte Carlo simulations showed that adding 28 housing units to the presently included 17 units would give 80% power for detecting a group difference in ReQoL of 8.8 points. Code from the simulations is included as supplementary appendix.

Framework

The present study is a superiority trial, and all statistical tests will be of null hypotheses of the two arms being equal with respect to corresponding estimand.

Statistical interim analysis and stopping guidance

After the first wave, the internal pilot will be analyzed with respect to outcome variability, intra-class correlation drop out rate, adherence and required sample size for the full-scale study. While being an internal pilot, and hence its data will be included in the final analysis of full-scale study, the analysis at this stage will be non-comparative with respect to the study arms. Therefore, no adjustments of significance level in final analysis will be made.

Should there be unexpected problems revealed by the internal pilot, e.g. feasibility problems or that it is shown that an unrealistic large sample size will be required for the study to be conclusive, there is opportunity to stop the study. This decision will be made by the investigators, and if so, the result from the internal pilot along with the motivation for stopping the study will be published. No official stopping rule has been predefined.

Timing of final analysis

All outcomes, primary and secondary, will be analyzed collectively after the locking of the database, when data collection is finished. The study project also involves cost effectiveness analyses of ELR. These analyses may be performed and published at different occasion than the analyses described in the present SAP.

Timing of outcome assessments

Measurements of ReQoL (primary outcome) RAS-DS (secondary outcome) will be conducted at baseline and at the 6-months follow-up, post-intervention. GAS, a secondary outcome, is only measurable for the intervention group at the 6-months follow-up.

Statistical principles

Confidence intervals and *P* values

A significance level of 5% will be employed in all hypothesis testing. The study includes one single primary outcome (ReQoL) and no adjustment to control for familywise type 1 error rate due to the multiple secondary outcomes will be performed. Precision of estimated parameters describing group differences will be assessed using 95% confidence intervals.

Adherence and Protocol deviations

Adherence to the intervention is defined as residents participating in at least 70% of the weekly sessions with occupational therapists. Further criteria for adherence are housing staffs completing the ELR education and housing managers asking the monthly follow-up questions at staff meetings. The adherence will be summarized and presented groupwise in the publication of study results. Violations of the study protocol will be included as an appendix to the published article of the final study.

Analysis populations

The primary analysis will use an intention-to-treat (ITT) approach and include all allocated participants with valid data, whether they did or did not receive the complete intervention.

A per-protocol population will be defined as participants following the adherence criteria listed under Adherence and Protocol deviations paragraph will also be made. The per-protocol population will be used for complementary, secondary analyses and presented in the study article.

Trial Population

Eligibility

Eligible participants are adults with severe psychiatric disability (SPD), living in sheltered or supported housing facility for people with SPD with access to occupational therapy.

Exclusion criteria are comorbidity of dementia or severe developmental disability, not being able to communicate in Swedish and currently being in acute psychosis, or acute suicidal risk.

Recruitment

In Figure 2, the planned information that will be reported in the flow chart of study participants is shown. Note that two more waves, wave 3 and 4, was added to reach sufficient power.

[figure not shown]

Figure 2. Draft of planned flow chart describing the enrollment, allocation and analysis of participants and housing facilities in the publication of the study. Note that two more wave, wave three and four was added to the study.

Withdrawal/ Follow-up

Participants, housing staff, occupational therapists or municipalities may choose to withdraw from the study at any point. Reasons for withdrawal will be summarized for both groups, along with the total frequency of participants lost to follow-up, in the publication of the study. Figure 2 shows draft of the information that will be reported in the flow chart.

Baseline patient characteristics

Baseline characteristics of both housing facility level and individual participant level will be presented by group, in line with Consort Statement (ref). In table 1 below, baseline variables to be presented are listed.

Table 1. Variables to include in table of housing facility and patient characteristics. Q1-Q3 – quartiles.

Variables at housing facility level	Comment/summary measure
Type of housing facility	Number/percentage
Variables at individual participant level	
Sex	Number/percentage
Age	Median (Q1-Q3)
Civil status	Number/percentage
Highest education	Number/percentage
Ethnicity	Number/percentage borned in Sweden
Diagnosis	Number/percentage
Number of years living in housing facility	Median (Q1-Q3)

Analysis

Outcome definitions

Primary Outcome Measure: Recovering quality of life score at 6-months follow-up(2). An increase of points on the ReQoL score denotes improvement. In ReQoL-20, the minimum score is 0 and the maximum is 80, where 0 indicates poorest quality of life and 80 indicates highest quality of life.

Secondary Outcome Measure: Perceived personal recovery and daily functioning, assessed using the Recovery Assessment Scale - Domains & Stages (RAS-DS) (3) at 6 months follow-up. A total recovery score is gained from adding the scores for all items. The minimum score is 0 and the maximum score is 152.

Secondary Outcome Measure: Goal Attainment at 6-months follow-up

Goal-attainment will be measured within the intervention group only, using the Goal Attainment Scaling (GAS)(4). The scale has 5 points representing different levels of mastery of the individual participant's goal, from -2 to +2, where a score of minus (-2 and -1) represents less change than expected, 0 represents the expected level of change/attainment, and plus (+1 and +2) represents achievement of more change than expected. GAS uses T-scores, where scores are rescaled so that T-scores have a mean of 50 and a standard deviation of 10. If all of the goals meet the expected level of achievement, the GAS T-score will be 50. A high T-score (50 or above) is reflective of expected or higher goal-attainment.

Only within-group changes will be analyzed. The GAS measurement is measured at the 6-months follow-up.

Analysis methods

Primary Outcome Measure (ReQoL):

A mixed effects models will be used. The dependent variable will be the ReQoL 6 months follow-up measurement. A random intercept effect for housing facilities will be included in the model. Fixed effects independent variables will be *group* (ELR or control) and *baseline ReQoL measurement*. The baseline ReQoL will be adjusted for, on both an individual participant level and on an aggregated cluster level using the average of the baseline measurement within the corresponding housing facility(5). The treatment effect is presented as the baseline-adjusted group effect at 6 months follow-up, along with its 95 % confidence interval.

Secondary Outcome Measure RAS-DS:

The same mixed effects models as for ReQoL is planned to be used. The dependent variable will be the RAS-DS 6 months follow-up measurement. A random intercept effect for housing facilities will be included in the model. Fixed effects independent variables will be *group* (ELR or control) and *baseline RAS-DS measurement*. The baseline RAS-DS will be adjusted for, on both an individual participant level and on an aggregated cluster level using the average of the baseline measurement within the corresponding housing facility. The treatment effect is presented as the baseline-adjusted group effect at 6 months follow-up, along with its 95 % confidence interval

Secondary Outcome Measure GAS:

GAS will be evaluated using paired t-test, comparing the pre- and post-intervention t-score.

Model assumptions

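### The Objectives claim effectiveness of ELR on goal attainment, but GAS is measured and tested in the ELR arm only, so this part of the objective has no comparator and the Framework statement does not fit it.

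*SAP*

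**What the plan says.** The SAP's Objectives section states a single overall objective, to "investigate the effectiveness on quality of life, self-perceived recovery, everyday functioning, and goal-attainment of ELR". Goal attainment stands beside quality of life, recovery and everyday functioning without any qualification.

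The Framework section calls the trial a superiority trial and says that "all statistical tests will be of null hypotheses of the two arms being equal with respect to corresponding estimand".

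Other sections treat goal attainment differently:

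- Timing of outcome assessments: "GAS, a secondary outcome, is only measurable for the intervention group at the 6-months follow-up".
- Outcome definitions, under goal attainment: "Only within-group changes will be analyzed".
- Analysis methods, under GAS: "GAS will be evaluated using paired t-test, comparing the pre- and post-intervention t-score".

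For ReQoL and RAS-DS, by contrast, Analysis methods specifies a mixed model with a group term and presents the baseline-adjusted group difference as the treatment effect.

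**The concern.** In a randomised trial, a claim of effectiveness rests on the contrast with the control arm. For GAS there is no such contrast. Any movement over six months in the ELR arm combines whatever ELR adds with whatever would have happened under usual care, and the design cannot separate the two.

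The SAP's own Background section makes the point. It describes earlier feasibility studies with pre-post measures, GAS among them, and then says that effectiveness still has to be established in a randomised trial. The GAS analysis repeats that uncontrolled pre-post contrast inside the randomised trial, under an objective worded as effectiveness.

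At stake is a non-randomised p-value reported under an effectiveness objective, possibly alongside null ReQoL and RAS-DS comparisons. Subgroup analyses and Additional analyses also extend all analyses to each sex and to the per-protocol population, so the same uncontrolled test would appear several times.

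**Working it through.** **1. Objective against analysis, domain by domain**

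| Component of the objective | Measure | Measured in TAU? | Planned contrast |
|---|---|---|---|
| Quality of life | ReQoL | Yes | ELR against TAU, mixed model |
| Recovery and everyday functioning | RAS-DS | Yes | ELR against TAU, mixed model |
| Goal attainment | GAS | No | Pre against post within ELR, paired t-test |

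The null hypothesis of the paired t-test is that the mean change in the ELR arm is zero. It contains no TAU quantity, so it cannot be a hypothesis that the arms are equal. The Framework sentence is therefore wrong for one of the two secondary outcomes. No section narrows the goal-attainment objective to description.

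**2. The plan's own figures**

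The SAP gives no sample size or power for GAS. Its original figure of 35 facilities per arm is for ReQoL and can be reproduced: 2 × (1.96 + 0.842)² × 10² / 5² = 62.8, so 63 participants per arm; the design effect is 1 + (2 − 1) × 0.1 = 1.1; 63 × 1.1 / 2 = 34.65, rounded up to 35. That figure is sound on its inputs but has no bearing on GAS.

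**3. How readily the paired test is significant without an ELR effect (illustration)**

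Inputs:

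- Number of ELR residents. Sample Size gives 17 + 28 = 45 facilities and an average of 2 residents each. Half of the 90 residents is 45. I also use 30 as a lower assumed value.
- SD of change in T-score: assumed 10 or 14. The SAP's SD of 10 describes the T-score itself, not its change.
- Shift that would occur without ELR: assumed 3, 5 or 10 T-points.
- Two-sided 5% level; clustering ignored; true ELR effect zero.

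Formula: with N residents, SD of change s and shift d, the noncentrality is λ = d / (s/√N). The rejection probability is P(|T| > t₀.₉₇₅,N−1), where T is noncentral t with N − 1 degrees of freedom and noncentrality λ.

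| N | SD of change | Shift 3 | Shift 5 | Shift 10 |
|---|---|---|---|---|
| 30 | 14 | 21% | 47% | 97% |
| 30 | 10 | 36% | 75% | 100% |
| 45 | 14 | 29% | 65% | 100% |
| 45 | 10 | 50% | 91% | 100% |

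The nominal 5% holds only if the shift without ELR is exactly zero.

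A single observed result shows the same thing. With N = 45 and SD of change 10, a mean rise of 4 points gives t = 4 / (10/√45) = 2.68 and p = 0.010 on 44 degrees of freedom. Nothing in that p-value says how much of the rise is due to ELR.

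**The case against.** The strongest reply is that the SAP is open about the limitation. It says in two sections that GAS concerns the intervention group only, labels it secondary, and uses treatment-effect language only for ReQoL and RAS-DS. Individual goals may also exist only under ELR, which would explain why TAU residents are not measured. All of this stands, and it rules out any suggestion of concealment. It does not explain why the objective still speaks of effectiveness on goal attainment, or why Framework says that all tests compare arms.

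A reader might go further than the documents allow in four ways:

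- *That a positive GAS result is close to guaranteed.* This is not shown. At an assumed 3-point drift the test is significant in only 21% to 50% of trials, and the SAP gives no drift. The direction and size of change also depend on the pre-intervention score, which the SAP does not define. That is a separate matter.
- *That the trial's objective cannot be answered.* Only one of the four listed domains lacks a comparator.
- *That season explains a GAS change across the trial.* Trial design gives the first two waves as "starting the intervention in September of 2021 and 2022, respectively". Start months for waves 3 and 4, which are to supply 28 of the 45 facilities, are not stated.
- *That TAU residents would show the same drift.* The SAP gives no information on this. The point is that it cannot be known, not that it is so.

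**Conclusion.** The point holds as a mismatch between objective and analysis for one secondary outcome. The goal-attainment component of the objective has no comparator, so a significant GAS result would not show an ELR effect, and the Framework sentence is incorrect for GAS. This rests on the SAP's text alone and needs no numerical assumption.

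The numerical size is illustrative only. The rates in the table depend on assumed numbers of residents, SDs of change and drifts. They show that the paired test can readily be significant without any ELR effect, not how often it would be in this trial. The primary analysis, the sample size and the randomised RAS-DS comparison are untouched.

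**What to change.** Change the wording in three places before the database is locked:

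1. **Objectives.** Limit effectiveness to the outcomes compared between arms, and add a separate aim such as: *to describe goal attainment at 6 months among residents receiving ELR*.
2. **Framework.** Restrict the null hypothesis of equal arms to ReQoL and RAS-DS, and say that GAS is descriptive.
3. **Analysis methods, GAS.** Replace the paired t-test with the ELR-arm mean 6-month T-score and its 95% CI, plus the share of residents at 50 or above. The CI should account for housing facility, for example through an intercept-only mixed model with a random facility intercept, fitted with the software already named. If the ReQoL planning values of 2 residents per facility and ICC 0.1 applied to GAS, the standard error would rise by √1.1 = 1.05, or about 5%. State that the result does not support a claim of effect, and apply the same rule wherever GAS appears in the subgroup and per-protocol analyses.

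This needs no new data and does not touch the randomised comparisons. The cost is a more modest claim for one secondary outcome.

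### Houses are randomised 1:1 within municipality, but the ReQoL and RAS-DS models omit municipality; if it is prognostic beyond baseline, the test is mildly conservative and a random intercept would recalibrate it

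*SAP*

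**What the plan says.** Under Randomization, the SAP fixes the design: "The randomization will be stratified on municipalities, giving a 1:1 allocating ratio of housing facilities within each participating municipality". It adds "Randomization will be performed separately at the two waves". The reason given for stratifying is practical, though only in part: "This is partly due practical reasons; the required education of occupational therapists and housing staff could be unfeasible" if too many houses in one municipality were in the intervention group. Recruitment later says "Note that two more waves, wave 3 and 4, was added to reach sufficient power". That waves 3 and 4 were also randomised separately is a natural inference, but it is not stated.

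Under Analysis methods, the ReQoL model has group and baseline ReQoL as fixed effects, with baseline entered at individual level and as the house mean. For the random part, "A random intercept effect for housing facilities will be included in the model". RAS-DS has the same structure. Model assumptions, Sensitivity analyses, Missing data and Statistical software add neither municipality nor wave. The SAP does not say why they are left out.

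**The concern.** When houses are balanced between arms within each municipality, differences between municipalities largely cancel from the arm comparison. A model without municipality does not know this. It assigns those differences to the house variance and charges them to the standard error of the arm effect. The reported interval is then wider than the sampling variation of the estimate warrants, and the test rejects a true null less often than 5%.

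This happens only if municipality is prognostic after both baseline terms. If it is not, the planned test is correct. At stake are the calibration of the primary and RAS-DS intervals and, at the larger assumed shares, a few points of power. Power was already scarce enough for the target difference to be moved from 5 to 10 points.

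**Working it through.** **1. The SAP's own figure.** With SD 10 and a difference of 5, an individually randomised comparison needs 63 per arm. The design effect is 1 + (2 − 1) × 0.1 = 1.1, and 63 × 1.1 / 2 = 34.65, so 35 houses per arm. The original sample size reproduces.

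**2. An SD consistent with the pilot.** The Sample Size section gives 53% power for 5 points with 70 houses. On a t-test with 68 degrees of freedom this implies an SE of 2.42. With 2 residents per house and ICC 0.1, SE = SD × √(2 × 1.1 / 70), so SD = 2.42 / 0.1773, about 13.66 before rounding the SE. For the revised plan ("adding 28 housing units to the presently included 17 units would give 80% power"), SE = 13.66 × √(0.55 × (1/22 + 1/23)) = 3.02. That gives about 81% power at 8.8 points by formula and 79.2–80.1% by simulation, close to the stated 80%.

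**3. Upper limit by arithmetic.** In units of total variance, a house mean has variance 0.1 + 0.9/2 = 0.55. Let municipality carry a share *s* of total variance, contained within the ICC of 0.1. With perfect balance the contrast sees only 0.55 − *s*, while the planned model uses about 0.55. The SE is then too large by the factor √(0.55 / (0.55 − *s*)), and in large samples the type I error is 2 × (1 − Φ(1.96 × factor)).

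- *s* = 2.5%: factor 1.024, type I error 4.5%
- *s* = 5%: factor 1.049, type I error 4.0%
- *s* = 10% (all between-house variance is municipality variance): factor 1.106, type I error 3.0%

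**4. Simulation with loss of houses.** The Sample Size section says "The average attrition rate of the ELR and TAU arms combined after wave 2 was 33" per cent. Random loss partly breaks the balance and so shrinks the effect. The setting was 68 houses randomised 1:1 in strata of four, two or eight, each municipality in one wave, 23 houses lost at random and 45 analysed. There were 20,000 runs per scenario (Monte Carlo error about ±0.3 points for type I error and ±0.6 for power). A house-mean baseline was in every model. The adjusted model has a random municipality intercept, fixed wave and Satterthwaite degrees of freedom. Ranges run over the three stratum sizes.

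| Municipality share | 0 | 2.5% | 5% | 10% |
|---|---|---|---|---|
| Planned: SE above true SD of the estimate | 0.7–1.3% | 1.6–2.6% | 3.4–3.8% | 6.1–7.2% |
| Planned: type I error | 4.6–4.7% | 4.2–4.6% | 3.9–4.0% | 3.6% |
| Adjusted: type I error | 4.9–5.2% | 4.9–5.1% | 4.6–4.8% | 4.5% |
| Planned: power at 8.8 points | 79.2–80.1% | 79.9–80.3% | 80.0–80.6% | 81.3–81.5% |
| Adjusted: power at 8.8 points | 78.5–79.8% | 79.9–80.3% | 80.6–81.6% | 82.9–84.5% |

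The planned figure is already slightly below 5% at share 0 because variance estimates are truncated at zero. The estimate itself does not become more precise: at a 5% share its true SD is 2.98/2.98/2.96 planned and 3.02/3.03/2.99 adjusted (strata of four/two/eight).

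**5. Wave.** A wave share of 2.5% alone gives planned type I error of 4.4–4.7%, indistinguishable from no effect. Dropping wave from the adjusted model gave type I error of 4.4–5.2% and power 0.4–1.4 points higher.

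**6. Whole municipalities lost.** Withdrawal/ Follow-up allows this: "Participants, housing staff, occupational therapists or municipalities may choose to withdraw from the study at any point". Surviving strata then stay balanced. With 44 houses analysed (16,000 runs), planned type I error is 3.6–3.9% at a 5% share and 3.1% at 10%, near the limits in step 3.

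**7. Municipality intercept without the wave question.** A smaller simulation with 45 analysed houses and a 10% share (Monte Carlo error about ±0.8 points), including municipalities that span waves, gave planned type I error of about 3.5–3.8%. A random municipality intercept moved it to about 5–6% and raised power from about 82% to 85–86%.

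**The case against.** The strongest reply is that nothing in the plan is invalid. The SAP never promises to adjust for strata, its stated reason for stratifying is largely practical, and the planned test holds its level. The SAP does not show that municipality is prognostic, and the house-mean baseline may absorb stable municipality differences. An assumed 5% share is half of all between-house variance, and 10% is all of it. At 2.5% the power gain is nil. All of this stands. It limits the point to a conditional gain in calibration, but it does not explain why a factor fixed by the design is absent from the model. Baseline means also need not capture differences that arise during follow-up.

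Two further limits stand. The simulations delete lost houses, whereas the primary intention-to-treat analysis uses MICE, so the percentages cannot be carried over to the imputed analysis. And the remedy is not free of risk: type I error reached 5.5% (planned 5.0%) with strata of two, whole municipalities lost and no municipality effect, and up to about 6% in the smaller simulation.

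A reader might infer that wave is an equal omission because randomisation was also separate by wave. The figures do not support that, and the SAP does not state that waves 3 and 4 were randomised separately.

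**Conclusion.** The point holds as a minor one. The stated model omits the factor on which houses are stratified. If municipality is prognostic beyond baseline, the SE is a few percent too large, and the 5% test runs at about 4% at an assumed 5% share and about 3.6% at 10%.

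A reader might infer a biased effect, inflated false positives or an underpowered trial. None follows: the error is on the conservative side, the contrast is unbiased, and power of the planned model at 8.8 points stays at about 79–82% in every scenario of the table. Nor would the change sharpen the point estimate; it corrects the SE.

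The direction is secure. The size rests on assumed numbers of municipalities, stratum sizes, variance shares and loss pattern, with SD 13.66, ICC 0.1 and 2 residents per house, and on analysed houses without imputation.

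**What to change.** Before database lock, add a random municipality intercept to both models, for example `lmer(REQOL_post ~ arm + baseline + house-mean baseline + (1|municipality) + (1|unit))`. Keep Satterthwaite degrees of freedom, include municipality in the MICE model, and report the currently planned model as a sensitivity analysis. If the sponsor prefers to leave municipality out, the SAP should say why.

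- Add wave as a fixed effect only if municipalities took part in more than one wave. Its benefit is not shown, and four waves cost three degrees of freedom.
- No separate rule is needed when municipality variance is estimated at zero, because the fit then equals the model without that term. With wave in the model, this occurred in 55–60% of simulated trials at share 0, 38–44% at 5% and 24–33% at 10%.
- Avoid municipality fixed effects where few houses per municipality are analysed. With 15 strata of four, 33% loss, a 5% share and SD 10, they raised the SE from 2.40 to 2.54.

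The cost is SAP wording, since municipality is known for every house. If municipality is not prognostic, power changes by about −0.7 to +1 point. Type I error may rise slightly above 5%, to about 5.5–6%, in small strata, so a simulation with the actual strata is worth running before the change is fixed.
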